9.2.1 Risk/Benefit and Ethical Assessment

The study explores the effect of BCT197 as add-on therapy to current therapies versus placebo added to SoC, thus all enrolled subjects will continue to receive standard of care for their severe acute exacerbation of COPD, including systemic corticosteroids and/or antibiotics, as defined by GOLD updated version 2015.

BCT197 thus far has been investigated in two healthy volunteer studies, as well as in a PoC study in COPD [CBCT197A2201] and in another PoC study in acute kidney injury (AKI) [CBCT197A2202]. Rash, gastrointestinal (GI) toxicity, hepatotoxicity, headache and dizziness are some of the class effects of p38 MAPK inhibitors.

In the multiple dose-ascending study [CBCT197A2101] the percentage of rash has been proportionately high in healthy volunteers treated with both placebo and BCT197 doses of [REDACTED].

In the CBCT197A2201 study in acute exacerbation COPD subjects, no acneiform rashes were observed.

The benefit/risk assessment of using BCT197 to treat COPD exacerbations is positive if BCT197 proves to be efficacious. COPD exacerbations can be life threatening, whereas the occurrence of a rash which is mild and transient in nature, is not serious compared with the COPD exacerbation. The risk to subjects in this study will be minimised by compliance with the inclusion/exclusion criteria, close clinical monitoring, including signs and symptoms related to the potential risks of p38 MAPK inhibitors for at least 25 weeks following the last dose of study medication. Additional stringent monitoring for inclusion in the study with specific observation for any class effects will be performed throughout the study.

9.3 Selection of Study Population

9.3.1 Inclusion criteria

1. Male and female adults aged ≥ 40 years
2. Written informed consent obtained prior to any study-related procedure
3. Presence of an active exacerbation of the ongoing COPD requiring hospitalisation for treatment:

*“A sustained worsening of the patient’s condition (dyspnoea, cough and/or sputum production/purulence), from the stable state and beyond normal day-to-day variations, that is acute in onset and necessitates a change in regular medication in a patient with underlying COPD that includes prescriptions of systemic corticosteroids and/or antibiotics **and** need for hospitalisation”.*

4. Subjects with a diagnosis of COPD with spirometry performed outside an exacerbation within the last 12 months prior to the Screening Visit
5. Current smokers or ex-smokers with a smoking history of at least 10 pack years (pack-years = [number of cigarettes per day x number of years/20])
6. A FEV1 < 65% of the predicted normal value
7. A **documented** history of at least one moderate or severe COPD exacerbation in the 12 months preceding the Screening Visit that required antibiotics and/or systemic corticosteroid (addition or increment on subject current use) as defined below:
 - *“A sustained worsening of the patient’s condition (dyspnoea, cough and/or sputum production/purulence), from the stable state and beyond normal day-to-day variations, that is acute in onset and necessitates a change in regular medication in a patient with underlying COPD that includes prescriptions of systemic corticosteroids and/or antibiotics **or** need for hospitalisation”*
 - Also, documented visits to an emergency department due to COPD exacerbation are considered acceptable to fulfil this criterion.
8. Current regular treatment for COPD (categories C and D according to GOLD guidelines, updated 2015) for at least 2 months prior to the Screening Visit with either:
 - Inhaled corticosteroids/long-acting β_2 -agonist combination, long-acting muscarinic antagonist without regular use of any short-acting bronchodilator (any short-acting bronchodilator allowed if used as needed [PRN]) or
 - Inhaled corticosteroids/long-acting β_2 -agonist combination, without regular use of any short-acting bronchodilator (any short-acting bronchodilator allowed if used PRN or
 - Inhaled corticosteroids/long-acting muscarinic antagonist combination, without regular use of any short-acting bronchodilator (any short-acting bronchodilator allowed if PRN) or

- Inhaled long-acting β_2 -agonist and inhaled long-acting muscarinic antagonist (with any PRN short acting bronchodilator) or
 - Subjects under monotherapy with long-acting muscarinic antagonist (with any PRN short acting bronchodilator).
9. Ideally, subjects should be screened, randomised and dosed on the same day. Where information is not available, the Screening period can be extended to a maximum of 24 hours before Randomisation and dosing.

9.3.2 Exclusion Criteria

1. Current diagnosis of asthma
2. Subjects who have already completed treatment for the current exacerbation of COPD
 - Subjects whose treatment for the current exacerbation (systemic corticosteroids or antibiotics) was initiated longer than 24 hours before Randomisation.
3. Subjects who have been treated with or require use of the following medications (Refer to [Table 10-1](#)):
 - A course of systemic steroids longer than 3 days for COPD exacerbation in the 4 weeks prior to the current exacerbation
 - A course of antibiotics for COPD exacerbation longer than 7 days in the 4 weeks prior to the current exacerbation
 - Phosphodiesterase type 3/4 (PDE3/4) inhibitors
 - Any p38 MAPK p38 inhibitor treatment)
 - Use of antibiotics for a lower respiratory tract infection (e.g. pneumonia) in the 4 weeks prior to the current exacerbation (except for treatment of the current exacerbation, but not longer than 2 days).
4. Subjects currently requiring intensive care unit (ICU) and/or mechanical ventilation
5. Subjects treated with non-cardioselective β -blockers in the 10 days preceding the Screening Visit. Those subjects may enter the study after non-selective β -blockers withdrawal and/or cardioselective β -blockers intake for at least 10 days before Randomisation
6. Subjects treated with long-acting anti-histamines unless taken at stable regimen at least 2 months prior to Screening and to be maintained constant during the study, or if taken as PRN
7. Known respiratory disorders other than COPD which may impact the efficacy of the study drug according to the investigator's judgement. This can include but is not limited to α -1 antitrypsin deficiency, active tuberculosis, lung cancer, bronchiectasis, sarcoidosis, lung fibrosis, pulmonary hypertension and interstitial lung disease
8. Subjects who have had pulmonary lobectomy or lung volume reduction surgery or lung transplantation

9. Subjects who have had a live vaccination in the last 30 days prior to study start
10. Subjects who have a clinically significant cardiovascular condition (including, but not limited to, unstable ischemic heart disease, New York Heart Association (NYHA) Class III/IV, left ventricular failure, acute myocardial infarction); or the current exacerbation is due to a cardiovascular condition
11. An abnormal and clinically significant 12-lead ECG which may impact the safety of the subject according to the investigator's judgement at Screening or Baseline
12. Subjects whose 12-lead ECG shows QTcF > 450 msec at Screening and at Randomisation visits; ECG does not need to be repeated if Screening and Randomisation visit are on the same day
13. Current diagnosis of pneumonia (clinical or radiographic), pulmonary embolus or pneumothorax
14. History of hypersensitivity to anti-cholinergics, β_2 -agonist, corticosteroids or any of the excipients contained in any of the formulations used in the study which may raise contraindications or impact the efficacy of the study drug according to the investigator's clinical judgement
15. Clinically significant laboratory abnormalities indicating a significant or unstable concomitant disease which may impact the efficacy or the safety of the study drug according to the investigator's clinical judgement
16. Subjects with liver enzyme alterations (serum alanine aminotransferase and/or aspartate aminotransferase > 2 x upper limit of normal [ULN], bilirubin > 1.5 ULN)
17. Impairment of renal function (defined as creatinine clearance [CrCL] < 60 mL/min [estimated by Cockcroft-Gault])
18. Concomitant/recent use of the CYP3A inhibitors or P-gp inhibitors including, but not limited to macrolide antibiotics troleandomycin, erythromycin, clarithromycin, roxithromycin and chloramphenicol (with the exception of azithromycin, which is not prohibited), and of the calcium channel blockers verapamil and diltiazem; consumption of grapefruit will also be excluded (Refer to [Table 10-1](#))
19. Unstable concurrent disease: e.g. uncontrolled hyperthyroidism, uncontrolled diabetes mellitus or other endocrine disease; significant hepatic impairment; significant renal impairment; uncontrolled gastrointestinal disease (e.g. active peptic ulcer); uncontrolled neurological disease; uncontrolled haematological disease; uncontrolled auto-immune disorders, or other which may impact the efficacy or the safety of the study drug according to the investigator's judgement
20. History of alcohol abuse and/or substance/drug abuse within 12 months prior to the Screening Visit
21. Participation in another interventional clinical study where the investigational drug was received within < 5 x half-lives of the drug or 8 weeks (whichever is longer) (6 months in

the case of a monoclonal antibody) prior to the Screening Visit. Participation in observational/non-interventional studies is allowed

22. Pregnant or nursing (lactating) women, where pregnancy is defined as the state of a female after conception and until the termination of gestation, confirmed by a positive urine test at Screening
23. Sexually active men unless they are using double barrier method for the period of dosing and the 5 half-lives (8 days) afterwards
24. Women of child-bearing potential, defined as all women physiologically capable of becoming pregnant, unless they are using highly effective methods of contraception during the study and for 8 days after treatment with investigational medication. Highly effective contraception methods include:
 - Total abstinence (when this is in line with the preferred and usual lifestyle of the subject. Periodic abstinence (calendar, ovulation, symptothermal, post-ovulation methods) and withdrawal are not acceptable methods of contraception
 - Female sterilisation (surgical bilateral oophorectomy with or without hysterectomy) or tubal ligation at least six weeks before taking study treatment. In case of oophorectomy alone, only when the reproductive status of the woman has been confirmed by follow-up hormone level assessment
 - Male sterilisation (at least 6 months prior to Screening). For female subjects on the study, the vasectomised male partner must be the sole partner for that subject
 - Combination of the following:
 - a) Use of oral, injected or implanted hormonal methods of contraception or other forms of hormonal contraception that have comparable efficacy (failure rate <1%), for example hormone vaginal ring or transdermal hormone contraception. In case of use of oral contraception women should have been stable on the same pill for 3 months before taking study treatment.
 - b) Placement of an intrauterine device (IUD) or intrauterine system (IUS).
 - Women are considered post-menopausal and not of child-bearing potential if they have had 12 months of natural (spontaneous) amenorrhoea with an appropriate clinical profile (e.g. age appropriate, history of vasomotor symptoms) or have had a surgical bilateral oophorectomy (with or without hysterectomy) or tubal ligation at least six weeks ago. In the case of oophorectomy alone, only when the reproductive status of the woman has been confirmed by follow-up hormone level assessment is she considered not of child-bearing potential. Sexually active men must use double barrier method while taking drug and for 5 half-lives (8 days) after completing investigational medication and should not father a child in this period. A condom is required to be used also by vasectomised men in order to prevent delivery of the drug via seminal fluid.

9.3.3 Withdrawal of Subjects from the Study

Subjects may voluntarily withdraw consent to participate in the study for any reason at any time.

Withdrawal of consent occurs when a subject does not want to participate in the study anymore and does not want to attend any further visits or assessments, have further study related contact, or allow analysis of already obtained biologic material.

If a subject withdraws consent, the investigator must make every effort to determine the primary reason for this decision and record this information. Investigational treatment must be discontinued and no further assessments conducted. All biological material that has not been analysed at the time of withdrawal must not be used. Further attempts to contact the subject are not allowed unless safety findings require communication or follow-up.

The investigator should discontinue participation of a given subject if, on balance, he/she believes that continuation would be detrimental to the subject's well-being. However the subject should be followed up to the end of the study and all study procedures should be performed per protocol. As a minimum, all assessments for Week 26 should be performed according to the Schedule of Assessments [Table 9-1](#).

9.3.4 Study Drug Discontinuation

Subjects may voluntarily discontinue investigational treatment for any reason at any time. Subject decision on discontinuation of study drug does not imply an automatic withdrawal from the study. If the subject does not want to take study drug but desires to continue in the study he/she may remain in the study and continue to undergo all assessments/procedures.

Investigational treatment must be discontinued under the following circumstances:

1. Emergence of the following adverse events:
 - Absolute QTcF > 500 msec
 - Occurrence of class effects i.e., rash Grade 4 as defined by exfoliations and ulcerations ([Galimont-Collen et al 2007](#))
2. Any of the following laboratory abnormalities:
 - Renal function values that require discontinuation:
 - Discontinue investigational treatment for a subject if individual serum creatinine increases $\geq 50\%$ compared to Baseline (and is considered clinically significant), or in the event of treatment emergent proteinuria (albumin:creatinine ratio (ACR) > 300 mg/g or >30 mg/mmol; protein creatinine ration (PCR) ≥ 500 mg/g or >50 mg/mmol), unless the event is not drug related, or if the benefit/risk assessment supports continuing investigational treatment
 - A renal event leading to subject discontinuation should be followed up until event resolution (serum creatinine within 10% of Baseline, protein-creatinine ratio within 50% of Baseline), stabilises or becomes not clinically significant, or is assessed as being chronic.

- Liver laboratory values that require discontinuation
 - ALT or AST > 5 times the ULN
 - ALT or AST > 3 times the ULN and bilirubin total > 2 times ULN or international normalised ratio (INR) > 1.5 or the appearance of worsening fatigue, nausea, vomiting, right upper quadrant (RUQ) pain/tenderness, fever, rash, or eosinophilia
- 3. Pregnancy as confirmed by a positive urine test at any time during Part 1 (Acute Exacerbation Phase)
- 4. Clinically significant change in cardiac rhythm or other clinically significant cardiovascular abnormality or an increase in QTcF \geq 60 msec above baseline
- 5. Use of prohibited treatment
- 6. Any other protocol deviation that results in a significant risk to the subject's safety
- 7. Withdrawal of informed consent.

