A preplanned interim analysis of Part B was conducted in October 2013 which included 66 subjects who had completed Day 5. At that time the AKI rate was higher on BCT197 [6/31 (19%)] than on placebo [2/33 (6%)], whereby AKI was defined as 25% or more reduction in eGFR at 48 hours. The reported (expected) control rate of AKI is in the 10 to 20% range. None of the subjects required dialysis. Furthermore, the number of subjects reporting SAEs in the BCT197 group [12 (36%)] was higher than that on placebo [3 (9%)], but these were distributed over several types of SAEs that were also expected in the cardiopulmonary bypass population. None of the SAEs was related to a kidney disorder and none was suspected to be related to study medication. The BCT197 group had an average baseline weight 9.1 kg heavier than the placebo group, suggesting that there may have been some degree of unbalanced randomisation. Based on the IA data, the Data Monitoring Committee (DMC) recommended to put the study on hold for reasons of lack of efficacy and the higher rate of SAEs on BCT197. According to the DMC the data did not allow assessment for a possible nephrotoxicity.

Based on the data available thus far, it appears that a regimen longer than a single dose would be required to sustain the effect of BCT197. Subjects will receive one of two oral dosing regimens of BCT197 or matching oral placebo administered according to the dosing schedules shown in [Table 7-1](#).

BCT197 is intended to be prescribed as a treatment added to standard of care (SoC) of acute exacerbations in COPD and is envisaged to be used for repeated administration. BCT197 is formulated as oral capsules. The two dose regimens proposed for this study are based on the efficacy, toxicology, pharmacokinetic and safety data available thus far. 

The rationales for the dose regimens proposed are based on the PK exposure and are explained in the [Section 7.2](#) below.

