12.3 Laboratory Assessments

Haematology, blood chemistry, and urinalysis will be conducted at Screening, on Days 1, 3, 5, 7, 10 and 14, and at each visit in the Stabilisation phase.

Haematology, blood chemistry and pregnancy tests done at the Screening visit of the study should be sent to both the local laboratory and central laboratory for analysis. Haematology, blood chemistry and pregnancy done at all other visits of the study should be sent only to the central laboratory for analysis, with the exception of urine dipstick pregnancy test that should be done at the local laboratory.

Local laboratory normal ranges will be collected prior to first patient first visit (FPFV) at each site and provided to data management via the study team. Laboratory results collected from the local laboratory should be entered in the eCRF by the investigator.

The following parameters will be assessed:

- Haematology: red blood cell count, white blood cell count with differential counts and percentages, total haemoglobin, haematocrit, platelets count, INR and prothrombin time (INR and prothrombin time not required during the Stabilisation phase)
- Blood chemistry: creatinine, blood urea nitrogen [BUN], fasting serum glucose, AST, ALT, gamma-glutamyl transpeptidase, total bilirubin, albumin, chloride, calcium, phosphorous, uric acid, total protein, sodium and potassium
- Urinalysis (specific gravity, pH, protein, glucose, blood)
- Pregnancy test: serum β -HCG and urinary pregnancy test.

Blood collection and sample preparation will be performed according to procedures from the local and central laboratories.

If sputum or bronchoalveolar culture is collected for any medical reason (qualitative or quantitative culture), the result should be recorded in the eCRF and included in the safety analysis.

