Parameter	Level for clinical concern
ALT	> 1.5 times the upper limit of the normal range (ULN) > 2xULN > 3xULN > 5xULN > 10xULN
AST	> 1.5xULN > 2xULN > 3xULN > 5xULN > 10xULN
Bilirubin Total	> 2xULN > 3xULN
ALT/AST and Bilirubin Total	ALT/AST > 3xULN and Bilirubin Total > 2xULN

Haematology, blood chemistry, pregnancy test results and qualitative urinalysis parameters (protein, glucose and blood) will be listed, including data from scheduled and unscheduled timepoints.

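### The proteinuria limb of the renal stopping rule rests on urine ratios that no scheduled test in the protocol or SAP measures, at Baseline or later

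*Protocol*

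**What the plan says.** Protocol 9.3.4 lists circumstances in which study drug must be stopped. The renal entry has two limbs. The first is serum creatinine: "Discontinue investigational treatment for a subject if individual serum creatinine increases" by at least 50% over Baseline and the rise is judged clinically significant. The second applies "in the event of treatment emergent proteinuria (albumin:creatinine ratio (ACR) > 300 mg/g or >30 mg/mmol", or when PCR reaches at least "500 mg/g or >50 mg/mmol), unless the event is not drug related" or a benefit/risk assessment supports continuing. A renal event that leads to discontinuation is followed until it resolves, defined as "serum creatinine within 10% of Baseline, protein-creatinine ratio within 50% of Baseline", or until it stabilises, loses clinical significance or is judged chronic.

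Protocol 12.3 gives the laboratory panel. Its urine entry is "Urinalysis (specific gravity, pH, protein, glucose, blood"; creatinine and albumin appear only under blood chemistry. The visit lists in Protocol 9.1.3 and the panel in SAP 8.7.2 repeat the same five urine items. In its reporting instructions SAP 8.7.2 says that "qualitative urinalysis parameters (protein, glucose and blood) will be listed".

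**The concern.** A mandatory stopping criterion should be defined by something the trial measures. Here the defining variables, ACR and PCR, are in none of the laboratory lists. A site that follows the schedule exactly will never hold a value to compare with the limit, and will have no pre-dose ratio against which to judge recovery.

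The point matters more because the programme carries an open renal question. In the earlier cardiac surgery study (Protocol 7.1), acute kidney injury was 6/31 (19%) on drug and 2/33 (6%) on placebo at the interim analysis, and "According to the DMC the data did not allow assessment for a possible nephrotoxicity". The present trial collects urine repeatedly and could add quantitative proteinuria data, but plans none.

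The mg/g and mg/mmol versions of each limit also do not convert into one another, so the same urine can fall on different sides of the limit depending on the unit the laboratory reports.

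**Working it through.** **1. Inputs to the renal rule compared with scheduled tests**

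| Input needed by Protocol 9.3.4 | Scheduled in Protocol 12.3 / SAP 8.7.2? |
|---|---|
| Serum creatinine, with Baseline | Yes, blood chemistry |
| Urine ACR | No (no urine albumin, no urine creatinine) |
| Urine PCR | No (urine protein described as qualitative; no urine creatinine) |
| Baseline PCR, for the resolution test | No |
| Reflex ratio after a positive urine protein | Not described |

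Urinalysis is scheduled at Screening, Days 1, 3, 5, 7, 10 and 14 and Weeks 8, 12 and 26: 1 + 6 + 3 = 10 time points. The number is up to 10 because Screening and Day 1 may coincide. The scheduled number of ACR or PCR values is 0.

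**2. Comparison with the liver rule in the same section**

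The laboratory inputs to the liver limits (ALT, AST, bilirubin, INR) are all in the Protocol 12.3 panel. SAP 8.7.2 also counts, by arm, subjects exceeding multiples of the upper limit of normal for ALT, AST and bilirubin. The proteinuria limb has neither the assay nor a table.

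**3. When a missing Baseline ratio matters**

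Protocol 12.1.1 and SAP 7.2.2.4 treat an event as treatment-emergent if it occurs or worsens on or after the first dose. If pre-dose urine protein is negative, a later ratio above the limit can reasonably be called emergent without a Baseline ratio. If protein was already present, worsening cannot be judged quantitatively. Exclusion criterion 17 sets a creatinine clearance limit but no criterion names a proteinuria limit, so such subjects can enter. The PCR resolution test needs a Baseline ratio in every case.

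**4. Unit pairs**

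The formula is mg/mmol = (mg/g) × M / 1000, with M the molar mass of creatinine. M is not in the documents; I assume 113.12 g/mol and tried 113.0 to 113.2.

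- ACR: 300 × 113.12 / 1000 = 33.9 mg/mmol (stated 30). In reverse, 30 × 1000 / 113.12 = 265 mg/g.
- PCR: 500 × 113.12 / 1000 = 56.6 mg/mmol (stated 50). In reverse, 50 × 1000 / 113.12 = 442 mg/g.
- Gap: 33.94 / 30 = 56.56 / 50 = 1.131, so the mg/g limit is 13% above the mg/mmol limit (13.0% to 13.2% over the range of M).

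An ACR above 265 and up to 300 mg/g, or a PCR above 442 and below 500 mg/g, meets the mg/mmol version and not the mg/g version. Exact agreement would need M = 30 / 300 × 1000 = 100 g/mol, which looks like rounding to a factor of ten. The PCR pair also mixes ≥ (mg/g) with > (mg/mmol).

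**The case against.** A reader might infer that the rule can never be triggered or followed up. The documents do not support that. Urine protein is scheduled on every dosing day, a positive result can prompt an unscheduled ratio, and Protocol 12.1.4 foresees additional diagnostic testing after an abnormal result. The serum creatinine limb works from scheduled data. Follow-up can end by stabilisation, loss of clinical significance or chronicity without any ratio. The rule also leaves room for judgement on drug-relatedness and benefit/risk. All of this stands. What it does not supply is a stated route to the ratio, or any way to recover a pre-dose value afterwards.

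A reader might also infer that the earlier study was put on hold for kidney toxicity. Protocol 7.1 gives the reasons as lack of efficacy and more serious adverse events, none of them a kidney disorder. Kidney injury there meant a fall in eGFR of 25% or more at 48 hours after bypass surgery, which is not proteinuria, and 6/31 against 2/33 gives a two-sided Fisher p of 0.14. The history shows an unresolved question, not a demonstrated harm.

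Nor is the trial blind to renal effects by arm. Serum creatinine is summarised with change from Baseline, urine protein is listed by regimen, and clinically significant abnormalities become adverse events. Only a quantitative proteinuria comparison is missing.

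With dosing on Days 1, 3 and 5 (Protocol 9.1.1), at most two doses remain to be withheld after the first. That limits the consequence, but it also leaves little time for an unspecified local test to come back.

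On units, the limits are joined by an or. Read literally, meeting either version suffices, which lessens the conflict.

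Finally, the laboratory manual is not among the documents. The protocol cites it only for the biomarker sample type (Table 9-1, note 11). If it does provide for ACR or PCR, Protocol 12.3 and the SAP would still need to say so.

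**Conclusion.** The point holds as an inconsistency between Protocol 9.3.4 and the laboratory panel in Protocol 12.3 and SAP 8.7.2. The proteinuria limb cannot be applied from scheduled data, because no ratio is planned at Baseline or on treatment and no reflex test is stated. This concerns one limb of one stopping rule; the creatinine limb is unaffected. It rests on the two documents being complete on this matter, since an unseen laboratory manual cannot be excluded.

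The 13% unit gap is real under the assumed molar mass, probably arises from rounding, and is secondary, as is the mixed operator in the PCR pair. Severity: should-fix. The documents do not show which limit is intended, and none is suggested here.

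**What to change.** - Reconcile Protocol 9.3.4 with Protocol 12.3 and SAP 8.7.2 so that the variable defining the proteinuria limb is measured. One way is to run urine albumin, protein and creatinine, reported as ACR and PCR, on urine already collected pre-dose and at the on-treatment laboratory visits. If the sponsor intends a reflex test instead, state what prompts it and how the Baseline ratio is obtained.
- Reconcile the mg/g and mg/mmol versions, and the ≥ and > operators, into one limit per ratio. The sponsor decides the limits.
- In SAP 8.7.2, add a by-arm count of subjects meeting the protocol's own creatinine and proteinuria limits, alongside the existing liver table.

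The cost is a wording change in the protocol and laboratory manual, a small assay charge on urine already taken, and one safety table. No visit or procedure is added.
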